Description of Study Design:	
This is a Phase 2/3, double-blind, randomized, placebo-controlled trial to test the safety and immunogenicity of two doses given 21 days apart of the IVAC A/H5N1 vaccine. In the Phase 2 study, 300 healthy adult subjects will be randomized to receive 15 mcg of vaccine (n=100), 30 mcg of vaccine (n=100), or saline placebo (n=100). Safety and immunogenicity will be assessed in all 300 subjects. Although full evaluation of the safety will continue through Day 91, there will be an early evaluation of the safety and immunogenicity data collected through Day 43 of Phase 2 to determine whether to proceed to Phase 3 and what dose to select.
 
A vaccine dose will be selected based on safety and immunogenicity using pre-specified criteria. The conduct of Phase 3 will be dependent on showing an HAI response titer of $\geq 1:40$ in 60% or more vaccine recipients in at least one of the two vaccine groups in Phase 2.
 
The dose selected from Phase 2 will be used in the Phase 3 trial. Phase 3 is a confirmatory study that will expand the safety and immunogenicity in a larger number of subjects to meet product registration in Vietnam. In Phase 3, subjects will be randomized to receive the vaccine dose selected in Phase 2 (n=1,000) or saline placebo (n=500) under double blind. Safety will be assessed in all subjects and immunogenicity will be measured in a subset of approximately 300 subjects receiving the IVACFLU-A/H5N1 (vaccinees) from 500 subjects enrolled at one of 3 study sites (Hai Phong) in Phase 3.
 
All subjects in Phase 2 and Phase 3 will receive two injections of A/H5N1 vaccine or placebo, 21 days apart. Subjects will be male and female healthy adults from 18 through 60 years of age.

Hypothesis:	
The study hypotheses are that:
 
 • Two 0.5 mL injections of whole virion monovalent A/H5N1 influenza vaccine (IVACFLU-A/H5N1) adjuvanted with alum will be safe and well tolerated in healthy adults, and • At least one of the two doses tested will be immunogenic in 60% or more of the subjects tested.

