All subjects in the Full Analysis population who have valid baseline (Day 1)¹ and a post-vaccination immunogenicity measure with no major protocol violations that are determined to potentially interfere with the immunogenicity assessment of the study vaccine. This population will serve as the primary analysis population for all immunogenicity objectives.

The criteria for exclusion of subjects from the Full Analysis Population and Per Protocol Population will be established by the study statistician and the study medical officer before breaking the blind and will be based on the blinded review of protocol violations.

III. MISSING DATA

In the event that missing dates or times are needed to compute durations of outcomes, the following rules will be applied:

- If the month and year are known, but the date is missing, the 15th will be used for any calculations of relative time (e.g., UNMAY2012 will become 15MAY2012).
- If only the year is known, but the month and date are missing, June 15th of the known year will be substituted for any calculations of relative time (e.g., UNUNK2011 will become 15JUN2011).
- If the minutes of start or stop times are missing, time will be assumed to be on the hour for a 24 hour clock (e.g., 11:UN, is assumed to be 11:00 AM).

If some safety data is available for the subject in safety population but respective data is missing then subject will be included in the analysis and data will be treated as follows:

1. For solicited AEs, if the severity for all 7 days are missing or the diary card was not completed or was marked as ‘unknown’ then the aggregated value will be set to missing and the subject will be excluded from the analysis. If the intensities are missing for only some of the days then the missing intensities will be evaluated as the maximum of the previous and next non-missing value for calculation of the aggregated value. For example if fever intensity is recorded as 1, (blank field), 2, 0, 0, for day 0 to day 4, then the missing day 2 intensity is imputed to be 2. Severity is missing for any AE then it will be considered as AE of maximum severity (Grade 3) “Severe” unless it’s captured as SAE. For SAE missing severity will be considered as maximum severity (Grade 4) “Life Threatening”
2. If “Relationship” is missing then it will be considered as “Related” to vaccine administered i.e. study vaccine/ placebo.

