Safety: To evaluate the safety and tolerability of two injections given 21 days apart of A/H5N1 vaccine at the dose level of 15 mcg.	
The safety profile of IVACFLU-A/H5N1 will be evaluated by the proportion of subjects experiencing AEs, related or not related, of the following five categories for all subjects and by age group (18-40 years of age and 41-60 years age):
 
• Number and percentage of subjects with solicited local and systemic adverse events within 30 minutes after each vaccination.• Number and percentages of subjects with solicited local adverse events (redness, swelling, pain, induration, and tenderness) over a 7-day period (Days 1-7; Days 22-28) post each vaccination.• Number and percentages of subjects with solicited systemic/general adverse events (fever, fatigue/malaise, muscle aches (generalized), joint aches, chills, nausea, vomiting, and headache) over a 7-day period (Days 1-7; Days 22-28) post each vaccination.

	
 Number and percentages of subjects with unsolicited adverse events for 21 days post each vaccination. All serious adverse events (SAEs) occurring over the entire study period. (Days 1-91).
Immunogenicity: To evaluate the immunogenicity of the A/H5N1 influenza vaccine as determined by serum HAI titer $\geq 1:40$ at Day 43 in a sample of approximately 270 subjects receiving the IVACFLUA/H5N1 (vaccinees) and placebo.	
Primary: Percentage of subjects achieving an HAI titer $\geq 1:40$ after the second vaccination on Day 43.
 
Secondary:
 
 The percentage of subjects achieving a seroresponse (at least a four-fold increase in post-vaccination titer) on Day 43 as determined by HAI. Geometric Mean Titer (GMT) of Day 43 as determined by HAI. Geometric Mean Titer Ratio (GMTR) of Day 43/Day 1 as determined by HAI.

II. ANALYSIS POPULATIONS

The need for different analysis populations depends on how well the protocol is followed by study personnel and participants as well as the objectives of specific analyses. The final statistical report will include an accounting of all persons screened, including the number enrolled, the number followed during the study, and other key study status indicators. The reason for excluding any data from any analysis population will be documented.

A. Enrolled Population

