All screened subjects who provide informed consent, regardless of the subject's randomization and treatment status in the trial.

B. Full Analysis (FA) Population

All subjects in the enrolled population who were randomized, received a study vaccination. This population will serve as the primary analysis population for all safety objectives. The immunogenicity analysis based on this population will serve as the supportive results for all immunogenicity objectives. Subjects who withdraw or are terminated from the study will be included in the FA data set until the time of withdrawal or termination. Subjects will be analyzed as received; that is, allocation errors, if any, are taken into account.

C. Per Protocol (PP) Population

All subjects in the Full Analysis population who have valid baseline (Day 1)¹ and a post-vaccination immunogenicity measure with no major protocol violations that are determined to potentially interfere

¹ The protocol does not state this requirement.

with the immunogenicity assessment of the study vaccine (e.g., missed the 2nd vaccination). This population will serve as the primary analysis population for all immunogenicity objectives.²

The criteria for exclusion of subjects from the Full Analysis Population and Per Protocol Population will be established by the study statistician and the study medical officer before breaking the blind and will be based on the blinded review of protocol violations.

III. MISSING DATA

In the event that missing visit dates or study contact dates are needed to be imputed for couples of study forms, the following rules will be applied:

- The month and year are known, but the date was missing, the 15th was used for any calculations of relative time (e.g., UNMAY2016 will become 15MAY2016).

For missing safety related data, the following rules will be applied:

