- For solicited AEs, if the severity for all 7 days are missing or the diary card was not completed or was marked as ‘unknown’ then the aggregated value will be set to missing and the subject will be excluded from the analysis. If the intensities are missing for only some of the days then the missing intensities will be evaluated as the maximum of the previous and next non-missing value for calculation of the aggregated value. For example if fever intensity is recorded as 1, (blank field), 2, 0, 0, for day 0 to day 4, then the missing day 2 intensity is imputed to be 2. Severity is missing for any AE then it will be considered as AE of maximum severity (Grade 3) “Severe” unless it’s captured as SAE. For SAE missing severity will be considered as maximum severity (Grade 4) “Life Threatening”
- If “Relationship” is missing then it will be considered as “Related” to vaccine administered i.e. study vaccine/ placebo.
- If for Start date - day of event / condition is missing for any adverse event then it will be imputed as the date of last dose of study vaccine / placebo.
- If for Start date - day and month of any adverse event is missing then it will be imputed as the date of first dose of study vaccine / placebo.
- If Stop date of any adverse event is missing then it will be treated as missing.

All immunogenicity assays reported below the limit of quantification (LLOQ, e.g. <1:10) will be assigned a value by the study lab. No missing data will be imputed.

² This definition is similar to the criteria: 1) the completion of a certain pre-specified minimal exposure to the treatment regimen; 2) the availability of measurements of the primary variable(s); 3) the absence of any major protocol violations including the violation of entry criteria; that given by ICH guideline E9: statistical principles for clinical trials: International Conference on Harmonisation of Technical Requirements for Registration of Pharmaceuticals for Human Use; 1998. Available from: <http://www.ich.org/products/guidelines/efficacy/article/efficacy-guidelines.html>.

IV. UNBLIDING STUDY CODE FOR FINAL DATA ANALYSES

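### The SAP dates an adverse event with an unknown start day to an undefined 'last dose', with no check against the recorded month or stop date, so the imputed onset can contradict the data.

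*SAP*

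**What the plan says.** Section III of the final SAP has three rules for incomplete AE dates.

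- Only the start day missing: "day of event / condition is missing for any adverse event then it will be imputed as the date of last dose".
- Day and month both missing: "day and month of any adverse event is missing then it will be imputed as the date of first dose".
- Stop date missing: "If Stop date of any adverse event is missing then it will be treated as missing". A recorded stop date is not used to limit the imputed start.

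The final SAP also has a rule that keeps the recorded month: "The month and year are known, but the date was missing, the 15th was used for any calculations of relative time". Its lead-in sentence limits that rule to visit and study contact dates.

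Section III of the interim SAP has the same last-dose rule for AE start dates: "it will be imputed as the date of last dose of study vaccine / placebo". It also has a mid-month rule for dates needed to compute durations of outcomes: "If the month and year are known, but the date is missing, the 15th will be used for any calculations of relative time". It does not say which rule governs an AE start date.

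On the schedule, the protocol summary says: "All subjects in Phase 2 and Phase 3 will receive two injections of A/H5N1 vaccine or placebo, 21 days apart". Among the outputs, the final SAP lists "Number and percentages of subjects with unsolicited adverse events for 21 days post each vaccination" as a safety endpoint (section I), and its AE listings show study day of onset and duration (section VIII).

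**The concern.** When only the day is missing, the month and year are known. The rule discards them in favour of a dose date that may lie in another month. Nothing stops it from placing the start after a stop date that is on record.

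The pair of rules is also oddly ordered. A record with less information (day and month unknown) goes to the first dose. A record with more information (month known) goes to the last dose, even if its month rules that dose out.

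Safety is a primary objective, and unsolicited events are reported by 21-day period after each vaccination. A wrong onset can put an event under the wrong dose, give a wrong study day, or produce a negative duration.

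**Working it through.** The plan gives no figure to reproduce, so the check applies the rule literally by date arithmetic.

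**Inputs from the documents.** Doses on Day 1 and Day 22; unsolicited AEs followed for 21 days after each dose (Days 1-42); serious adverse events (SAEs) followed over Days 1-91.

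**Assumptions not in the documents.** Onset is uniform over the days considered. Day 1 takes each calendar date of 2016 (366 days) in turn. Illustrative AE durations are 1, 3, 7 and 14 days. All percentages are conditional on the start day being missing.

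**Example.** Doses on 16 May and 6 June 2016; an AE truly starts on 20 May and is recorded as May 2016, day unknown. If the last dose is dose 2, the start becomes 6 June. That is 17 days late, in the wrong month, under the wrong dose, and after the stop date if the event ended before 6 June.

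**Reading A: last dose = dose 2 (Day 22).**

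- Shift for onset on Day k: |22 - k|. Days 1-21 give 21 down to 1 (mean 11). Days 22-42 give 0 to 20 (mean 10). Overall mean 10.5, maximum 21.
- No shift is as long as a month, so a shift of j days crosses a month boundary for about 12 × j / 366 of calendar dates. On average this is 12 × 10.5 / 366 = 126/366 = 0.344. The imputed month contradicts the recorded month in 34%. Full enumeration also gives 0.344.
- All events with onset on Days 1-21 are re-dated to dose 2.
- An event of duration d starting on Day k stops on Day k + d - 1. The imputed start is later than the stop when k ≤ 22 - d. Out of 21 onset days:

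| Duration (days) | Onset days affected | Start after stop |
|---|---|---|
| 1 | 21 | 100% |
| 3 | 19 | 90% |
| 7 | 15 | 71% |
| 14 | 8 | 38% |

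- SAEs on Days 43-91 move back 21 to 69 days, mean (21 + 69)/2 = 45. The recorded month is contradicted in 97% by enumeration.

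**Reading B: last dose = the most recent dose before onset.**

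- Mean shift over Days 1-42 is 10.0. Month contradiction is 12 × 10 / 366 = 120/366 = 0.328, or 33%.
- No event changes dose, and no start falls after its stop.
- The SAE figures for Days 43-91 are as in Reading A.
- The reading is not always workable. Both doses fall in one calendar month for 1 - (12 × 21)/366 = 31% of Day 1 dates, and an unknown day may then leave the preceding dose undeterminable.

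The month contradiction therefore occurs under both readings. The change of dose and the start-after-stop records occur only under Reading A.

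**The case against.** The strongest reply is that the harm is small and partly a matter of reading. The SAP does not say that the last dose is dose 2, and under Reading B neither the dose shift nor the negative durations arise. Partial dates should also be uncommon. Onset time is a required AE item (protocol 9.2.1), AEs are reviewed at Days 8, 22, 29 and 43, SAEs are reported within 24 or 48 hours (9.3.1), and questionable data are queried (13.3, 15.1). Solicited reactions come from diary cards and have their own missing-data rule. No test is planned for unsolicited AEs or SAEs.

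Much of this stands and limits the size of the problem. It does not rescue the rule, which can contradict a recorded month under Reading B too, and the ambiguity is itself a defect. The pairing with the first dose in the next rule makes dose 2 the more natural reading.

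Several stronger conclusions are tempting, but the documents do not support them.

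- Day 22 falls in a different month from Day 1 for 69% of Day 1 dates (252/366). That is a share of calendar dates, not of events; the share of partial-date events contradicted is about a third.
- A shift above 21 days does not follow from doses 21 days apart. It needs a late second visit: up to 25 days with the +4 window in protocol 4.6.3, or 23 with the +2 window in 7.3.5.
- Re-dating a late SAE does not change the SAE endpoint, because Day 22 lies inside Days 1-91.
- Relatedness is a clinician's judgement (protocol 9.2.3), and nothing says it is re-derived from an imputed date.
- The final SAP does not have two competing rules for AE dates. Its mid-month rule covers visit and contact dates only, so the overlap is confined to the interim SAP.

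**Conclusion.** The concern holds as a defect in a stated rule: an AE start with only the day missing can be given a date that the record itself excludes. About a third of partial-date events on Days 1-42 would contradict their recorded month (34% or 33%), assuming uniform onset. If the last dose means dose 2, all first-dose-period events with an unknown day in two-dose subjects are also moved to dose 2. Of these, 38% to 100% would start after they stopped, for durations of 14 days down to 1.

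The effect is limited to listed study day of onset, duration and any by-dose AE split, and to events with partial dates, whose frequency is not stated. Whole-study AE counts, the Day 1-91 SAE count and the immunogenicity endpoint do not change. This should be corrected, but it does not threaten the trial's main conclusions.

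**What to change.** In section III of the final SAP, replace the rule for AE start dates with only the day missing:

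1. Impute within the recorded month and year, never after the recorded stop date.
2. If a dose was given in that month on a date compatible with the stop date, use that dose date. Otherwise use the first day of the month.
3. State which dose is used when both fall in the month and the stop date does not settle it.
4. Flag these records in the listings as having an imputed onset.

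In the interim SAP, make the same change and state that it takes precedence over the 15th-of-month rule for AE start dates.

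Month contradictions and start-after-stop records then disappear by construction. Dose attribution remains a convention. With doses on 16 May and 6 June, an event that ran from 2 to 10 June with its start day unrecorded would still be dated 6 June. The flag is there to make such cases visible.

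The cost is one paragraph in each SAP and a few lines of code, with no new data.

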A four-fold rise was observed from baseline to post first vaccination in 11 (35.5%) and 12 (37.5%) subjects for low dose vaccine and high dose vaccine, respectively. The number of subjects reporting a 4-fold rise increased from baseline to post-vaccination 2 with 21 (67.7%) and 23 (71.9%) subjects responding in low dose vaccine and high dose vaccine, respectively. However, not all vaccinees with a 4-fold rise reached a titer of 1:40 (**Table 7**) because titers rising from baseline (1:5) to 1:20 were considered a 4-fold rise. Twenty (31.7%) subjects had a 4-fold rise between post-vaccination 1 and post-vaccination 2 with 9 (29.0%) subjects in low dose vaccine and 11 (34.4%) subjects in high dose vaccine. All 95% CIs at each time point showed a significant difference from placebo, but a significant difference was not observed between low dose vaccine and high dose vaccine at any time point.

The GMT's and GMFR's in the vaccine groups were significantly higher (i.e., the lower bound of the 95% CI for the GMT/GMFR ratio > 1.0) than placebo, but there was not a difference in GMT's or GMFR's between the low dose vaccine and high dose vaccine group at either dose (**Table 8**).

Similar to the seroconversion rates, there was no difference in the GMTs according to dose. In the combined high and low dose vaccine groups the GMT was 12.3 after one dose and 25.8 after two doses. The mean fold rise in the combined vaccine group was 5.2.

Table 8: Geometric mean HAI titers after first dose on Day 21 and after the second dose on Day 42

Dose	No. of subjects	Day 0	Day 21	Day 42	HI fold increase after 2 doses
High dose	32	5.0	11.9	27.1	5.4
Low dose	31	5.0	12.8	24.5	4.9
Combined	63	5.0	12.3	25.8	5.2
Placebo	12	5.0	5.0	5.0	1.0

Serum Neutralizing Antibodies (Microneutralization): Four (12.9%) subjects from low dose vaccine and 6 (18.1%) subjects from high dose vaccine achieved an MNT titer $\geq 1:40$ after vaccination 1. The number of subjects achieving the MNT titer $\geq 1:40$ after vaccination 2 increased to 11 (35.5%) and 13 (40.6%) subjects for low dose vaccine and high dose vaccine, respectively. No placebo subjects reported MNT titer $\geq 1:40$ at any visit.

Table 9. Neutralizing Antibody Titer (MNT) immune response (titer $\geq 1:40$) rates after two doses of vaccine measured on Day 0, 21, and 42

Dose group	No. of subjects	Number (%) with MNT titer ≥ 40		
		Day 0	Day 21	Day 42
High dose	32	0	6 (18.1)	13 (40.6)
Low dose	31	0	4 (12.9)	11 (35.5)

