8.2.2 Immunological Assays

Serum Antibody to Influenza Virus Detected by HAI

The HAI assay is the most frequently used serologic test for determining immunologic response to influenza vaccination. Serum specimens will be tested for the presence of HAI antibodies to influenza by the National Institute of Hygiene and Epidemiology (NIHE), in Vietnam. Briefly, sera are pretreated with heat and a receptor-destroying enzyme to reduce non-specific inhibition. In 96-well micro titer plates, serum specimens are then serially diluted using 2-fold dilutions and incubated with standardized titers (typically 4 AU) of influenza virus antigens representing vaccine strain. After incubation, red blood cells (RBC) are added to individual wells and allowed to sediment. Plates are tipped, and RBCs that have settled will produce a streak (RBCs run or flow), indicating inhibition of hemagglutination and the presence of serum antibodies against the influenza test strain. Wells with lattice formation (hemagglutination) will not streak. When processing paired sera (pre- and post-vaccination), an increase in antibody titer indicates response to vaccination. The choice of RBC is particularly important for detecting antibodies to A/H5N1 virus. Chicken RBCs which are typically used in HAI assays are not very sensitive to H5N1 and should not be used. Instead, horse-derived RBCs are preferred and will be utilized after appropriate screening of horse donors. If no suitable donor is available, RBC from turkey may also be used in this assay.

The HAI assay will be conducted in serum samples from all the subjects in Phase 2 of the study and in a subset of approximately 300 subjects receiving the IVACFLU-A/H5N1 (vaccinees) from one study site in Phase 3. For this assay, serum specimen collection will occur on Days 1, 22 (Phase 2 only), and 43. On Days 1 and 22, collection must take place prior to administration of the study product.

Serum Antibody to Influenza Virus Detected by Microneutralization Assay (MNT)

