Percentages of subjects with immune response will be calculated along the corresponding two-sided exact (Clopper-Pearson) binomial CIs. GMT and GMTR will be summarized by treatment group along with the corresponding two-sided 95% CIs, by exponentiating the corresponding log-transformed means and their 95% CIs. Titers below the lowest limit of quantitation (i.e., below the starting dilution of assay reported as “< 10”) will be set to half that limit (i.e., $10 / 2 = 5$). For Phase 2, two-sided 95% CIs for the difference in proportions of participants demonstrating seroresponse between the two dose groups will be based on the Newcombe hybrid score (METHOD=SCORE riskdiff-option for PROC FREQ in SAS). For the GMT and GMFR, two-sided 95% confidence intervals (95% CIs) for the ratios post-vaccination GMTs/GMFRs between two dose groups will be constructed using a log-normal distribution. The log values will be used to construct a 95% CI using t-distribution for the mean difference between the two treatment groups. Then the mean difference and the corresponding 95% CI limits will be exponentiated to obtain the GMT ratio and the corresponding CI. No comparisons will be made between the IVACFLU-A/H5N1 dose groups and the placebo group in both Phase 2 and Phase 3.

This study has a single primary endpoint and it maintains the experiment-wise Type I error rate at 2-sided of 0.05. No multiplicity adjustment to the error rate, alpha, will be made for secondary immunogenicity endpoints. Also no imputation of missing immunogenicity measures will be made.

13 Data Capture Methods

CRFs will be developed and data will be managed to the extent possible in accordance with internationally agreed-upon standards, such as the Clinical Data Acquisition Standards Harmonization, which defines basic standards for the collection of clinical trial data, and/or The Society for Clinical Data Management’s Good Clinical Data Management Guidelines.

All the information required by the study protocol must be recorded on the CRF provided by the sponsor, or if it is laboratory assay data, transferred in a format agreeable to the sponsor. All data must be entered legibly, as described in any *CRF Completion Guidelines*. An explanation must be provided for any missing data. Data entered onto the CRFs must be accurate, legible, contemporaneous, original (or traceable to the original source), and attributable.

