It is possible that samples fall below the cut-off or LLQ of some antigens. Values below the cut-off of the assay will be given an arbitrary value of half the LLQ for the purpose of the calculation. Similarly, for lab value above MDL an arbitrary value of 2-fold the MDL will be given for the purpose of the calculation. The final details about the cut-off values will be provided by the study lab.

For each group and at each time-point (Day 1, Day 22 and Day 43) that a blood-sample result was available following descriptive analyses were performed:

- Frequencies and proportions of available specimens, valid immune responses and measurements below/above certain cut-off will be tabulated.
- GMTs and their 95% confidence intervals (CIs) will be calculated by taking the anti-log of the mean of the log concentration or titer transformations.
- Distributions of antibody titers (log scale) will be displayed using reverse cumulative distribution curves.
- The reasons for excluding from the immunogenicity analysis will be listed.

VII. ANALYSIS OF IMMUNOGENICITY OBJECTIVES

All immunogenicity endpoint analyses and summaries will be performed on a per-protocol basis for all subjects and by age group (18-40 years of age and 41-60 years age). Supportive analysis will also be conducted on participants in the FA population who received at least one dose of study vaccines if the difference in the number of subjects between the FA and PP populations exceeds 5%.

Objective: To evaluate the immunogenicity of two different doses (15 mcg and 30 mcg) of A/H5N1.

² Horne AD, Lachenbruch PA, Getson PR, and Hsu HS Analysis of Studies to Evaluate Immune Response to Combination Vaccines. Clinical Infectious Diseases 2001; 33(Suppl 4):S306-11

There are two types of immunogenicity endpoints, percentages of subjects with immune response and Geometric Mean Titers (GMT), will be used to evaluate this study objective.

Percentages of subjects with immune response:

- Percentage of subjects achieving an HAI titer $\geq 1:40$ ³ on Day 43. (primary endpoint)
- Percentage of subjects with a serum HAI titer $\geq 1:40$ at Day 22.
- Percentage of subjects demonstrating an HAI seroresponse of at least a four-fold increase in postvaccination titer on Day 22 and Day 43.
- Percentage of subjects with at least a four-fold rise in titer at Day 22 and Day 43, as determined by microneutralization (MN).

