Following information on enrollment will be summarized by study group for FA Population; baseline demographics, medical history, vital signs, pregnancy test and general physical examination. Baseline measures are those obtained closest to but preceding randomization and vaccine #1. No inferential statistics (e.g. p-values, confidence intervals) will be computed comparing treatment groups on baseline variables.

D. Laboratory Data

The immunogenicity measures will be expressed by Hemagglutination Inhibition (HAI) titers and also expressed as geometric mean titer (GMT) of the antibody response. Because titers are often approximately lognormally distributed, they are customarily analyzed on a logarithmic (log) scale; a difference in arithmetic means on a log scale becomes a ratio of geometric means when the results of analysis are converted back to the original data scale.³

It is possible that samples fall below the cut-off or LLQ of some antigens. Values below the cut-off of the assay will be given an arbitrary value of half the LLQ for the purpose of the calculation. Similarly, for lab value above Method detection limit (MDL) an arbitrary value of 2-fold the MDL will be given for the purpose of the calculation. The final details about the cut-off values will be provided by the study lab.

For each group and at each time-point (Day 1 and Day 43) that a blood-sample result was available following descriptive analyses were performed:

- Frequencies and proportions of available specimens, valid immune responses and measurements below/above certain cut-off will be tabulated.
- GMTs and their 95% confidence intervals (CIs) will be calculated by taking the anti-log of the mean of the log concentration or titer transformations.
- Distributions of antibody titers (log scale) will be displayed using reverse cumulative distribution curves.
- The reasons for excluding from the immunogenicity analysis will be listed.

VII. ANALYSIS OF IMMUNOGENICITY OBJECTIVES

Objective: To evaluate the immunogenicity of the A/H5N1 influenza vaccine as determined by serum HAI titer $\geq 1:40$ at Day 43 in a sample of approximately 270 subjects receiving the IVACFLUA/H5N1 (vaccinees) and placebo.

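### Final SAP VI.D ties the above-range titre rule to the method detection limit, a lower-limit term, and no document names or values an upper limit of quantification

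*SAP*

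**What the plan says.** Final SAP, section VI.D (Laboratory Data), deals with both ends of the titration in consecutive sentences. At the low end, "Values below the cut-off of the assay will be given an arbitrary value of half the LLQ for the purpose of the calculation". At the high end, introduced as a parallel case, "for lab value above Method detection limit (MDL) an arbitrary value of 2-fold the MDL will be given for the purpose of the calculation". The paragraph closes with "The final details about the cut-off values will be provided by the study lab". The list below it adds that "measurements below/above certain cut-off will be tabulated" and calls for reverse cumulative distribution curves of the titres.

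Interim SAP, section VI.D, has the same high-end rule without spelling out the abbreviation: "for lab value above MDL an arbitrary value of 2-fold the MDL will be given for the purpose of the calculation".

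The protocol has a rule for the low end only. Section 12.4.3 sets a result below the starting dilution of 10 to 5. Section 8.2.2 says that for HAI "serum specimens are then serially diluted using 2-fold dilutions", but states no top dilution. The MN description in the same section gives none either.

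The titres feed GMT and the Day 43/Day 1 ratio (GMTR or GMFR), which are secondary endpoints in both phases. The primary endpoint is the percentage with HAI of 1:40 or above at Day 43.

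**The concern.** The rule is meant for results beyond the top of the assay, but the Final SAP anchors it to a term that ordinarily names the bottom. Followed to the letter, it replaces measured, in-range titres by one fixed low number. The low end already has its own limit (the LLQ), so the paragraph is left with two low-end terms and no upper one.

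At stake are the GMT and GMFR of the Phase 3 vaccine group, their confidence intervals, the reverse cumulative curves, and any pooled Phase 2 and Phase 3 summary that the Final SAP allows if needed. There is also a practical risk. The numerical cut-offs are left to the laboratory, and a laboratory asked for its MDL could reasonably return a low-end figure.

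**Working it through.** **Inputs**

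- Low-end code: below 10 is set to 5 (Protocol 12.4.3). The SAPs also word the low-end value in other ways in their sections III; that is a separate matter, and 5 is used here.
- Titre grid: two-fold steps from 10, i.e. 10, 20, 40, 80 and so on (Protocol 8.2.2 and 12.4.3).
- Phase 1, 15 mcg arm (Protocol 2.1.3, Tables 7 and 8 and text): n = 32; all below 10 at baseline; four-fold rise after dose 2 in 23; HAI of 1:40 or above in 18; GMT 27.1; fold rise 5.4.
- MDL: no value is given anywhere. The main case assumes 10, the starting dilution; other values follow.

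**The protocol's own figures reproduce.** 27.1/5.0 = 5.42 (stated 5.4); 24.5/5.0 = 4.9; 25.8/5.0 = 5.16 (stated 5.2); 23/32 = 71.9%; 18/32 = 56.3%.

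**Step 1: who is at 20 or above.** The protocol says that "titers rising from baseline (1:5) to 1:20 were considered a 4-fold rise". With every baseline at 5, a four-fold rise is the same as a titre of 20 or more. So 23 of 32 are at 20 or above, and the other 9 are at 5 or 10.

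**Step 2: apply the rule with MDL = 10.** A titre above 10 becomes 2 × 10 = 20. A titre of exactly 10 is not above the limit and is kept. The 23 therefore become 20, and the 9 stay at 5 or 10.

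- All 9 at 5: GMT = 5 × (20/5)^(23/32) = 5 × 4^0.719 = 13.5; fold rise 13.5/5 = 2.7.
- All 9 at 10: GMT = 10 × (20/10)^(23/32) = 10 × 2^0.719 = 16.5; fold rise 16.5/5 = 3.3.

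The same calculation for the combined arms (44 of 63 at 20 or above) gives 13.2 to 16.2 against the reported 25.8. For the 7.5 mcg arm (21 of 31) it gives 12.8 to 16.0 against 24.5.

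**Step 3: four-fold response.** 20/5 = 4, so the same 23 subjects count as responders. The rate does not change at MDL = 10.

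**Step 4: other values of the limit, 15 mcg arm**

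| Assumed limit | Effect on titres | GMT (reported 27.1) |
|---|---|---|
| 5 | all detectable titres become 10 | 5 × 2^(23/32) = 8.2, up to 10.0 |
| 10 | 20 and above become 20 | 13.5 to 16.5 |
| 20 | above 20 become 40 | 20.0 to 24.3 |
| 40 | above 40 become 80 | capped; counts at 80 and above not given |
| 640 (a possible top dilution) | 10 to 640 kept; above 640 becomes 1280 | 27.1 remains attainable |

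For the limit of 20, the counts are 18 at 40, 5 at 20 (23 − 18) and 9 at 5 or 10. The bounds are 5 × 2^((18×3 + 5×2)/32) = 5 × 2^2 = 20.0 and 5 × 2^((54 + 10 + 9)/32) = 5 × 2^(73/32) = 24.3.

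**Step 5: the 1:40 threshold.** With a limit of 20 or more, a titre of 40 or above stays at 40 or above after substitution, so the rate is unchanged. With 10 or 5, no substituted value reaches 40, so the rate would depend on whether reported or substituted titres are scored.

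**The case against.** The best reply is that nobody would run the rule literally. The paragraph already has the LLQ for the low end, and the next sentence is framed as its mirror image. Results above as well as below a cut-off are to be tabulated, and a reverse cumulative curve would be pointless if nearly all titres were one number. Both SAPs have the programs and tables verified with blinded group codes before the unblinded run, and tables with no titre above 20 would be noticed. If the limit is in fact an upper one above 1:40, the rule touches only off-scale results. The threshold endpoint and four-fold status from 5 are then unaffected, and GMT and GMFR could shift only by an amount the documents do not let us estimate.

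All of this stands as evidence of intent and as a reason to think a literal run unlikely. It does not correct the term. Leaving the cut-offs to the laboratory does not cure it either, because the SAP names the wrong quantity to ask for. Even on the kindest reading, the upper limit has no value and no date by which it must be fixed.

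A reader might infer that both SAPs make the same error and that the Phase 2 dose choice was exposed. The documents do not support this. The Interim SAP never expands MDL, so there the term is undefined rather than shown to be a lower limit. The Final SAP, which contains the wrong term, already states 15 mcg as the selected dose.

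**Conclusion.** The Final SAP is wrong as written on this point; the Interim SAP uses an undefined term. On the assumption that MDL equals the 1:10 starting dilution, and with Phase 1 data as illustration, a literal application roughly halves the 15 mcg GMT (13.5 to 16.5 instead of 27.1) and takes the fold rise from 5.4 to between 2.7 and 3.3. These figures show the effect of following the text; they do not forecast the trial's results.

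Three stronger inferences are tempting and should not be drawn:

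- **That the primary endpoint would be 0%.** Section VI.D gives the substitution for calculation purposes, in the descriptive part. Section VII defines the endpoint by HAI titre and does not say that substituted values are scored.
- **That every detectable titre collapses to one value, with a GMT of up to 20.** That needs an MDL below 10, and 2 × MDL is then below 20. At MDL = 10 a titre of 10 is kept and the ceiling is 16.5.
- **That four-fold response would be inflated.** At MDL = 10 it is unchanged.

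**What to change.** In Final SAP VI.D, replace the method detection limit by the upper limit of quantification (ULOQ), defined as the highest dilution tested. Define the term the same way in Interim SAP VI.D. In both, state that titres from LLOQ to ULOQ are used as measured, and that only results the laboratory reports as above the ULOQ take the fixed value of 2 × ULOQ. State also that the 1:40 endpoint is scored on the reported titre, which closes the remaining ambiguity. Obtain the laboratory's ULOQ for HAI, and for MN where it is tested, and record it before unblinding.

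The cost is a sentence or two in each SAP and one figure per assay from the laboratory. No new data, samples or change to the sample size are needed.
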